#### [Aim 2 Outcomes](#)

##### [Overview](#)

Aim 2 is to evaluate the preliminary effects of PARTNER-MH on patient engagement, patient activation, and SDM.

Aim 2 has three main outcome measures: patient activation, patient engagement, and SDM. In addition, sociodemographic data (e.g., age, sex, race, ethnicity, education, and marital status) were collected at baseline. Tertiary and health-related outcomes that included communication self-efficacy, depression, mental health, and physical health functions were also assessed at all time points and are listed in the *Tertiary Outcomes* section.

### *Secondary Outcomes*

The *Patient Activation Measure for Mental Health (PAM-MH)* [37] is a 13-item questionnaire that measures an individual's perceived ability to manage illness and health behaviors. The PAM-MH is reliable, valid, and sensitive to change and correlates with measures of improved self-management and health outcomes. The questions are rated on a 4-point Likert-type scale and then converted using Rasch analysis to a 100-point scale. The PAM-MH has strong test-retest reliability and internal consistency (Cronbach  $\alpha=.91$ ).

Patient engagement will be assessed using the *Altarum Consumer Engagement (ACE)* measure, a 12-item measure that consists of 3 subscales to reflect patients' commitment to everyday health behaviors, navigation skills in using health care services, and informed choice in treatment decisions [38]. The ACE is administered as a 5-level Likert scale. The subscale scores range from 5 to 25, and the total engagement score is computed by adding the 3 subscale scores and multiplying the sum by 4/3 to obtain a possible range score of 20 to 100. Higher scores represent higher patient engagement.

Finally, we will administer the *SDM-Q-9*, a widely used 9-item patient-reported SDM measure that focuses on the decisional process by rating providers' behaviors in medical encounters. For this study, we will ask participants to think of their most recent visit with their mental health provider. The scale shows good internal consistency ( $\alpha=.94$ ) and high face and structural validity [39,40]. The SDM-Q-9 is rated on a 6-point Likert scale. The items are scored from 0 to 5 on a 6-point Likert scale ranging from "completely disagree" (0) to "completely agree" (5). A simple sum score with possible values between 0 and 45 is obtained. Item means range from 2.9 to 3.81, and the mean sum of SDM-Q-9 is 3.15 (SD 0.9) [41]. In addition to the SDM-Q-9, we added four questions to evaluate patient participation in treatment decision-making: (1) To the extent that SDM took place during your visit, how much did you drive the process? (2) Thinking about your goal for the visit (what you wanted to be done), how much do you feel you accomplished? (3) How much did you feel heard during your discussion with your provider? (4) Did you experience any barriers that kept you from speaking up or participating in SDM during that visit?

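### Do the ACE and SDM-Q-9 scoring statements fail to give the score scales that the plan reports?

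*Combined protocol and SAP*

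**What the plan says.** Both statements are in the Secondary Outcomes section of the combined protocol and SAP.

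**ACE (patient engagement).** The instrument is described as "a 12-item measure that consists of 3 subscales", and on responses the plan says "The ACE is administered as a 5-level Likert scale". Scoring begins at subscale level: "The subscale scores range from 5 to 25, and the total engagement score is computed by adding the 3 subscale scores", then "multiplying the sum by 4/3 to obtain a possible range score of 20 to 100". The section does not give the numeric coding of the five levels, the number of items in each subscale, or the step that turns item responses into a subscale score. It cites a source for the instrument.

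**SDM-Q-9 (shared decision-making).** This is "a widely used 9-item patient-reported SDM measure". The trial's own scoring is explicit: "The items are scored from 0 to 5 on a 6-point Likert scale", and "A simple sum score with possible values between 0 and 45 is obtained". The section then reports item means of 2.9 to 3.81 from a cited study and adds that "the mean sum of SDM-Q-9 is 3.15 (SD 0.9").

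The power statement, under Planned Statistical Analyses for Aim 2, uses PAM-MH with an SD of 14. It gives no figure for ACE or SDM-Q-9.

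**The concern.** ACE and SDM-Q-9 are two of the three main Aim 2 measures, and a reader who checks either description meets a number that does not fit.

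For ACE, twelve items in three subscales average four items each. Four items coded 1 to 5 sum to 4 to 20, not 5 to 25. An analyst who summed the items and then applied the only multiplier given would get a total of 16 to 80 instead of 20 to 100. Means and differences would then be too small on the stated scale.

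For SDM-Q-9, a sum that can reach 45 is paired with a mean of 3.15. Anyone using 3.15 (SD 0.9) as a reference for the sum would be wrong by a factor of nine.

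A pilot's means and SDs are natural inputs for planning a later trial, so a scale error here could be carried forward.

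**Working it through.** **Inputs, all from Secondary Outcomes.** ACE: 12 items, 3 subscales, 5 response levels, subscale range 5 to 25, multiplier 4/3, total range 20 to 100. SDM-Q-9: 9 items scored 0 to 5, sum 0 to 45, item means 2.9 to 3.81, quoted mean 3.15 (SD 0.9).

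**1. ACE rule as written.** Total = (sum of 3 subscale scores) × 4/3.
- Minimum: 3 × 5 × 4/3 = 20.
- Maximum: 3 × 25 × 4/3 = 100.

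The plan's own range is reproduced exactly.

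**2. Where 16 to 80 comes from.** It needs two things the plan does not state: items coded 1 to 5, and subscales formed as plain item sums. It also has to set aside the stated 5 to 25 range.
- Item sum: 12 × 1 = 12 to 12 × 5 = 60.
- Times 4/3: 16 to 80.

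**3. What would link items to the stated subscales.** Assume four items per subscale, coded 1 to 5.
- Raw subscale: 4 to 20.
- Times 5/4: 5 to 25.
- Three subscales added, times 4/3: 20 to 100.

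One ordinary rescaling step therefore makes the whole description consistent. That step is missing from the text. The stated ranges are not contradicted.

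**4. Effect if the step were missed.** With four items per subscale, each rescaled subscale is 1.25 times its raw sum, so the unrescaled total is 1/1.25 = 0.8 of the intended total. A true difference of 10 would appear as 8. The SD and standard error shrink by the same 0.8:
- t = (0.8 × difference) / (0.8 × SE), which is unchanged.
- Standardised effect = (0.8 × difference) / (0.8 × SD), which is unchanged.

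The repeated measures ANOVA tests are likewise unaffected by a constant factor.

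**5. SDM-Q-9.** The mean of a sum equals the sum of the item means.
- Lower bound: 9 × 2.9 = 26.1.
- Upper bound: 9 × 3.81 = 34.29.

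A mean sum of 3.15 lies outside 26.1 to 34.29, but 3.15 lies inside the item-mean range of 2.9 to 3.81. It is an item-level mean. On the sum scale it is 9 × 3.15 = 28.35, or about 28.4.

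The SD cannot be converted without knowing what 0.9 describes. If it is the SD of each person's mean item score, the sum has SD 9 × 0.9 = 8.1. If it is a typical single-item SD, the plan's alpha of .94 gives an average inter-item correlation r from 0.94 = 9r / (1 + 8r). Then r = 0.94 / 1.48 = 0.635, and the sum has SD 0.9 × √(9 + 72 × 0.635) ≈ 6.7.

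**6. Is either figure used?** The detectable differences in the plan are for PAM-MH: 0.965 × 14 = 13.5 between groups, 0.626 × 14 = 8.8 within the intervention group, and 0.778 × 14 = 10.9 within the control group (the plan prints 10.8). None involves ACE, 3.15 or 0.9. The planned models are fitted to the trial's own scores.

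**The case for a change.** The best case for acting is that the ACE shortfall does not depend on coding items 1 to 5. Twelve items with five unit-spaced levels span 12 × 4 = 48 points under any such coding, whereas three subscales of 5 to 25 span 3 × 20 = 60, and 48/60 = 0.8. The text gives only the 4/3 multiplier, so nothing in it stops an analyst from omitting the other step. The harm would fall on raw means, raw differences and comparison with other studies, which matter most from a pilot. For SDM-Q-9, the contradiction is proved from the section's own figures. Both corrections would be cheap.

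The arithmetic stands. Two parts of the conclusion do not. First, the plan supplies a check on ACE: an analyst who skipped the rescaling would get subscale scores that disagree with the stated 5 to 25 and totals that disagree with 20 to 100. Nothing in the documents suggests that the scoring code makes this error. Replacing the ranges with 4 to 20 and 16 to 80 could break a scale that is now consistent from the subscale level upward. Second, the plan states no detectable difference for SDM-Q-9. At d = 0.965, an SD of 0.9 would give 0.87, and SDs of 6.7 to 8.1 would give about 6.4 to 7.8, but the plan offers none of these, so there is no design figure to correct.

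**Conclusion.** No change to the plan follows. The ACE rule gives 20 to 100 from the subscale range it states. What is missing is the item-to-subscale step, a detail that analysts can fill sensibly from the instrument's scoring and check against the two printed ranges. The SDM-Q-9 label is a clerical slip: 3.15 is an item mean, about 28.4 on the sum scale. It sits beside a clear and correct 0 to 45 scoring rule, and nothing in the design or analysis draws on it.

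The effect on the sample size, the stated PAM-MH detectable differences and the planned tests is nil. The primary aim is feasibility and acceptability, which neither scale measures.

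This rests on three assumptions. The cited ACE source, which was not available here, supplies the subscale scoring. The scoring code follows it. For the claim that a missed step would leave tests and standardised effects exactly unchanged, the subscales have equal numbers of items; with an unequal split, omitting the rescaling would also alter the weight of each subscale. Anyone who later borrows the SDM-Q-9 reference values should find out in the cited study what the SD of 0.9 describes before converting it, since the sum-scale SD could be about 6.7 or 8.1.

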### *Tertiary Outcomes*

*Loneliness* was assessed using the University of California Los Angeles Loneliness Scale Short Form, a 6-item scale with a 4-point Likert scale ranging from 1 (never) to 4 (often). It has demonstrated internal consistency ( $\alpha=.89\text{-.94}$ ) and test-retest reliability ( $r=0.73$ ) [42].

The *Perceived Efficacy in Patient-Physician Interaction-5 (PEPPI-5) scale* measures patients' self-efficacy in obtaining medical information and attention to their chief health concern from a physician [43]. The PEPPI-5 is 5-item scale scored on a 5-point Likert scale ranging from 1 (not confident at all) to 5 (very confident). Higher scores indicate higher levels of self-efficacy. The PEPPI-5 has internal consistency ( $\alpha=.92$ ) and adequate test-retest reliability.

The *Working Alliance Inventory-Short Revised* evaluates three key aspects of the therapeutic alliance between patients and their mental health providers: (1) agreement on the tasks of therapy, (2) agreement on the goals of therapy, and (3) development of an affective bond [44,45]. The *Working Alliance Inventory-Short Revised* includes 12 items rated on a 5-point Likert scale ranging from 1(never) to 5(always). It shows good psychometric properties in both outpatient and inpatient populations, with a reliability of Cronbach  $\alpha>.90$  and convergent validity with the helping alliance questionnaire ( $r>0.064$ ).

The *Patient Health Questionnaire-9* measures the severity of depressive symptoms. The *Patient Health Questionnaire-9* includes 9 items and demonstrates high internal consistency and reliability (Cronbach  $\alpha=.89$ ) and good sensitivity and specificity for identifying cases of depression and assessing depression symptom severity [46].

The *Veterans RAND 12-item Health Survey* measures physical function, social function, role limitations owing to physical and emotional problems, mental health, energy and vitality, bodily pain, and the general perception of health. The *Veterans RAND 12-item Health Survey* uses 5-point ordinal response choices and provides two scores: the physical component summary score and the mental health summary score [47].

The *Perceived Discrimination in Healthcare Questionnaire* is a 7-item questionnaire that assesses a respondent's overall health care experiences rather than a specific experience based on their racial background. Respondents are asked to rate their experiences on a 5-point Likert-

type scale, with answers ranging from 0 (never) to 4 (always). This questionnaire has shown excellent reliability in diverse patient populations [48].

*Veterans' trust in the VA* is assessed using a 3-item questionnaire. Responses range from strongly

#### *Planned Statistical Analyses for Aim 2*

Power calculations are provided, but as a pilot, this study is powered only to detect large differences between groups. With a sample of 22 participants in the intervention group and 15 in the wait-list control group, we have 80% power at a .05 significance level to detect an effect size of 0.965 for tests between groups using 2-sided 2-sample *t* tests. With an estimated SD of 14 for PAM-MH based on previous studies, this sample size will allow detection of a PAM-MH difference of 13.5 between the 2 groups. Within the intervention group, the study can detect an effect size of 0.626 for tests between time points using 2-sided paired *t* tests, for a difference of 8.8 for PAM-MH changes. Similarly, in the wait-list control group, the study can detect an effect size of 0.778 and a difference of 10.8 for PAM-MH changes. To account for 25% attrition during follow-up, the study enrolled 30 intervention participants and 20 wait-list control participants. Figure 2 shows the participant flow.

The internal consistency of each scale for primary and secondary outcomes will be verified in this study sample using Cronbach  $\alpha$ . Distributions of the scale scores will be examined to determine whether transformation of the data or nonparametric tests are required for the analyses. In this study, 2-sample *t* tests and Fisher exact tests for continuous and categorical variables, respectively, will be used to compare the demographic and baseline data between participants with and without complete data. Repeated measures ANOVA (RMANOVA) for the scale scores will be used to compare data among the assessments over time. The RMANOVAs will allow different correlations between each assessment time and will allow for the appropriate covariance structure to model the intraparticipant correlations; they will also include a random effect for peers to account for correlation among participants with the same peer. In this intent-to-treat analysis, the RMANOVAs will provide unbiased estimates under the missing-at-random assumption. A 5% significance level will be used for each test.

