### Randomization and Protection Against Sources of Bias

Participants completed baseline assessment before being randomized into the study arms to ensure balance and reduce selection bias. Allocation to the treatment arm was carried out using a computer-generated randomization list with randomly varying block sizes of 4 and 8 to maximize allocation concealment. Furthermore, although blinding was not feasible for this project because of the study's limited staffing and the need to collect participant feedback on the feasibility and acceptability of the intervention, study personnel involved in screening and enrollment were masked to the computer-generated randomization assignment and were not included in delivering the intervention. Moreover, peers were not involved in data collection and did not have access to participants' assessment results.

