### Data Collection Methods, Data Management, and Monitoring

The data collection for this study is ongoing. Screening, enrollment, and survey data were collected and stored via VA REDCap (Research Electronic Data Capture; Vanderbilt University), behind the VA firewall. Outcomes were assessed over the phone at baseline and at 3, 6 (primary end point), 9, and 12 months. Outcome data also included qualitative interviews to evaluate participants' experience of the intervention and organizational factors that may impact its future implementation and the integration of the quantitative and qualitative data. Study participants were compensated with a US \$35 gift card for each assessment except for the primary end point (at 6 months), for which they received a US \$50 gift card. In addition, because of the COVID-19 in-person visit restrictions, participants received a US \$10 gift card for each month they remained enrolled in the study to facilitate access to telehealth delivery of the intervention and retention. A brief exit survey was sent to participants who discontinued the

study to evaluate their experiences in the program. Participants' enrollment in the study was recorded in their medical records, which peers had access to. A data safety and monitoring board was also established to evaluate the data quality and safety of the study.

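### The Aim 2 analysis names no baseline adjustment and no between-arm contrast, so the precision available from the pre-randomisation scores is not secured

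*Combined protocol and SAP*

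**What the plan says.** All references are to the combined protocol and SAP.

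- **Power, in Planned Statistical Analyses for Aim 2.** The evaluable sample is given as "With a sample of 22 participants in the intervention group and 15 in the wait-list control group". The claim for it is "we have 80% power at a .05 significance level to detect an effect size of 0.965 for tests between groups". The test is described as "for tests between groups using 2-sided 2-sample *t* tests", with no covariate. The scale is set by "With an estimated SD of 14 for PAM-MH based on previous studies", and the result is that "this sample size will allow detection of a PAM-MH difference of 13.5 between the 2 groups". For paired tests within the intervention arm, an effect size of 0.626 is converted to points: "for a difference of 8.8 for PAM-MH changes". The control arm has 0.778 and 10.8 points.
- **Outcome analysis, same section.** A repeated measures ANOVA of scale scores compares the assessments over time, with flexible within-participant covariance and a random effect for peers. The section names no baseline covariate, no constraint on the baseline means and no arm contrast.
- **Timing, in Data Collection Methods, Data Management, and Monitoring.** "Outcomes were assessed over the phone at baseline and at 3, 6 (primary end point), 9, and 12 months".
- **Baseline, in Randomization and Protection Against Sources of Bias.** "Participants completed baseline assessment before being randomized into the study arms to ensure balance and reduce selection bias". Blocks of 4 and 8 are described; stratification is not.

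**The concern.** Every participant has a baseline score that randomisation cannot have affected. With 37 evaluable people and a detectable difference close to one SD, that score is a cheap source of precision. The plan does not commit to using it.

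The two natural readings of the repeated measures ANOVA both fall short. If arms are compared on follow-up scores alone, baseline is ignored. If the contrast is arm by time with baseline means left free, it is a change-score comparison. That is less precise than an adjusted comparison at any correlation below 1, and less precise than ignoring baseline when the correlation is below 0.5.

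The two readings also react to a chance baseline difference in opposite directions. Leaving the contrast unstated therefore leaves open which estimate is reported.

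**Working it through.** **Inputs from the Aim 2 analysis section:** 22 v 15 evaluable, 30 v 20 enrolled, SD 14, two-sided 5% level, 80% power. **Assumed:** the baseline-to-month-6 correlation ρ, which the documents do not give. The calculations take complete data at 22 v 15, equal SDs at both times and no peer clustering.

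**1. Reproduce the plan's figure.** Exact noncentral-t power for d = 0.965 with 35 df is 80.0%. The detectable difference is 0.965 × 14 = 13.5 points. Both match.

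**2. The correlation implied by the plan.** The within-arm figures give change SDs of 8.8/0.626 = 14.06 and 10.8/0.778 = 13.88. Since SD(change) = 14 × √(2(1 − ρ)), ρ = 1 − 14.06²/(2 × 14²) = 0.50 and 1 − 13.88²/(2 × 14²) = 0.51. So ρ is about 0.5.

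**3. Standard error of the month-6 arm difference.** With k = √(1/22 + 1/15) = 0.335:

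- follow-up only: 14k = 4.69
- change from baseline: 14k√(2(1 − ρ))
- baseline-adjusted: 14k√(1 − ρ²)

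**4. Detectable difference at 80% power.** The multiplier is 13.51/4.69 = 2.88 with 35 df, and almost the same with the 34 df left after adjustment. The upper adjusted figure allows for estimating the baseline slope, which multiplies the variance by about 1 + 1/33 and the detectable difference by 1.015.

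| ρ | Follow-up only | Change from baseline | Baseline-adjusted | Adjusted power at 13.5 points, before slope cost |
|---|---|---|---|---|
| 0.4 | 13.5 | 14.8 | 12.4 to 12.6 | 86% |
| 0.5 | 13.5 | 13.5 | 11.7 to 11.9 | 90% |
| 0.6 | 13.5 | 12.1 | 10.8 to 11.0 | 94% |

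At ρ = 0.5 the variance factor is 1 − 0.25 = 0.75. Before the slope cost, that is the precision of about 37/0.75 = 49 evaluable participants.

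**5. Chance imbalance.** The baseline arm difference with 30 v 20 has SD 14 × √(1/30 + 1/20) = 4.0 points, and it exceeds 5 points in either direction in about 22% of randomisations. At ρ = 0.5 a 5-point imbalance moves a follow-up-only difference by 0.5 × 5 = 2.5 points. It moves a change-score difference by (0.5 − 1) × 5 = −2.5 points.

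**The case against.** The strongest reply is that the t test belongs to the sample-size calculation, where it is a common simplification that does not fix the analysis. The outcome analysis is a repeated-measures model whose assessments appear to include baseline. If baseline is a response, its information is used, and at ρ = 0.6 even a change contrast (12.1) beats 13.5. The document also refers readers to a published protocol paper, which may say more. This stands to the extent that one cannot state as fact that the comparison will be unadjusted; the documents show only that no adjustment is specified. It does not rescue the plan, because neither natural reading reaches the adjusted precision, and at the implied correlation the change contrast gains nothing.

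Four stronger readings are tempting but unsupported:

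- **Bias.** A reader might infer that the estimate is biased. Under randomisation the unadjusted difference is unbiased, and its standard error already allows for chance imbalance.
- **Imbalance set directly against 13.5 points.** Comparing the spread of baseline differences with a month-6 effect treats ρ as 1. Only the share ρ carries over, and only in a follow-up-only comparison.
- **A false claim about balance.** The stated purpose of ensuring balance can be read as attaching to randomisation rather than to the timing of the assessment, so that sentence need not be removed.
- **Adjustment as the only source of precision.** There are four follow-up assessments, and pooling them could also gain precision, though for a different contrast.

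**Conclusion.** The point holds as a free improvement of moderate severity. At a correlation near 0.5, either natural reading detects about 13.5 PAM-MH points, and an adjusted analysis about 11.7 to 11.9, with no new participants. The size of the gain rests on the assumed correlation. The value of 0.5 is only implied by the plan's use of an SD of about 14 for scores and for changes, and the planners may simply have reused one SD.

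A reader might infer that the trial's conclusions are invalid without this change. The documents do not support that. The primary aim is feasibility and acceptability, reported descriptively; Aim 2 is preliminary; and the plan says that it is powered only for large differences. Adjusted detectable effects at ρ of 0.4 to 0.6 are still about 0.77 to 0.90 SD (10.8/14 to 12.6/14). What is at stake is the width of the interval around the Aim 2 estimates and a clear prior choice of contrast.

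**What to change.** In Planned Statistical Analyses for Aim 2:

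1. Name the between-arm estimate for each scale as the month-6 arm difference with its 95% CI.
2. Take it from the planned longitudinal model, with baseline and follow-up scores as responses and the arm means constrained equal at baseline. The alternative is baseline score by visit as a covariate.
3. Beside the unadjusted 13.5 points, state the adjusted detectable difference over assumed correlations of 0.4 to 0.6: about 12.6, 11.9 and 11.0 after the slope cost.

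The cost is a few lines of text and no new data. The covariate version uses up to four degrees of freedom per scale, one for each follow-up visit. The document describes data collection as ongoing, so on its own account the choice can still be fixed before the outcome analysis.

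### Do the within-arm detectable PAM-MH changes (8.8 and 10.8) need correcting because they use an SD of 14 without a stated correlation between assessments?

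*Combined protocol and SAP*

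**What the plan says.** The power paragraph in Planned Statistical Analyses for Aim 2 gives three detectable effects, all at 80% power and a two-sided 5% level.

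- **Between groups.** "With a sample of 22 participants in the intervention group and 15 in the wait-list control group", the detectable effect size is 0.965. The conversion to scale points starts "With an estimated SD of 14 for PAM-MH based on previous studies", and "this sample size will allow detection of a PAM-MH difference of 13.5 between the 2 groups".
- **Within the intervention arm.** "Within the intervention group, the study can detect an effect size of 0.626" "for tests between time points using 2-sided paired" t tests, which the plan converts to a change of 8.8 points.
- **Within the control arm.** "in the wait-list control group, the study can detect an effect size of 0.778 and a difference of 10.8 for PAM-MH changes".

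The SD of 14 is the only SD the plan gives for this outcome. The plan does not say whether it describes scores or changes, and it states no correlation between assessments. The Secondary Outcomes section adds that "The PAM-MH has strong test-retest reliability and internal consistency". The coefficient printed there (0.91) is Cronbach's alpha; no test-retest coefficient is given.

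**The concern.** In a paired t test the effect size is the mean change divided by the SD of change. That SD equals the SD of scores only when the two assessments have equal variance and correlate at 0.5. The plan takes the SD it has just used to compare scores between arms and multiplies both paired effect sizes by it, with no comment. A measure described as strongly reliable over retesting might be expected to correlate above 0.5, in which case the detectable changes would be smaller than printed.

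The control-arm figure also fails as plain multiplication: 0.778 × 14 does not give 10.8.

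PAM-MH is one of the three main Aim 2 outcomes and the only one with detectable differences in scale points. A reader who wants to know which within-arm change this pilot could have detected would use these numbers and could misjudge the answer.

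**Working it through.** **Inputs, all from the Aim 2 power paragraph:** 22 intervention and 15 control participants with data; 80% power; two-sided 5% level; SD 14; 25% attrition.

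**1. Effect sizes.** Solve for the standardised effect *d* at which the noncentral t distribution gives 80% power. The noncentrality parameter is *d*√(n₁n₂/(n₁+n₂)) with n₁+n₂−2 degrees of freedom for two samples, and *d*√n with n−1 degrees of freedom for pairs.

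| Test | Plan | Recomputed |
|---|---|---|
| Two-sample, 22 and 15 | 0.965 | 0.9648 |
| Paired, n = 22 | 0.626 | 0.6264 |
| Paired, n = 15 | 0.778 | 0.7780 |

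All three reproduce.

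**2. Conversion with SD 14.**

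- 0.965 × 14 = 13.51; the plan prints 13.5, which agrees.
- 0.626 × 14 = 8.76; the plan prints 8.8, which agrees.
- 0.778 × 14 = 10.89; the plan prints 10.8, where rounding gives 10.9.

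Rounding of the inputs does not explain the last figure. Allowing for rounding of both printed numbers, 8.8 with 0.626 implies an SD between 8.75/0.6265 = 13.97 and 8.85/0.6255 = 14.15. Likewise 10.8 with 0.778 implies an SD between 10.75/0.7785 = 13.81 and 10.85/0.7775 = 13.95. The ranges miss each other narrowly. Truncation does not explain it either, since 8.76 would then print as 8.7. So it is a slip in the last digit.

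**3. Size of the slip.** 10.89 − 10.80 = 0.09 points on a 100-point scale. A true change of 10.8 with an SD of change of 14 and n = 15 has power of 79.3%.

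**4. The correlation.** If 14 is the SD of scores at each assessment, the SD of change is 14√(2(1−r)). The documents give no r, so each r below is an assumption.

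| Assumed r | SD of change | Detectable change, intervention (0.626 × SD) | Detectable change, control (0.778 × SD) |
|---|---|---|---|
| 0.3 | 16.57 | 10.4 | 12.9 |
| 0.5 | 14.00 | 8.8 | 10.9 |
| 0.7 | 10.84 | 6.8 | 8.4 |
| 0.8 | 8.85 | 5.5 | 6.9 |

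The figures are sensitive to r, and they move in both directions around the implied 0.5.

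**5. What depends on the within-arm figures.**

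- *Enrolment:* 22/0.75 = 29.3, rounded up to 30, and 15/0.75 = 20. Both follow from the sample sizes and attrition alone.
- *Hypothesis:* the one stated under Study Objectives is between groups, and its calculation (0.965 and 13.5) reproduces.
- *Analysis:* the repeated-measures model allows the correlation to differ between assessment times and estimates it from the data, so 0.5 is not carried into any result.
- *Primary aim:* feasibility and acceptability, reported descriptively.

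**The case for a change.** The strongest case for a change is that the claimed 80% power holds only near r = 0.5, and the reader is not told so. For the printed changes of 8.8 and 10.8, power is about 66% and 65% at an assumed r of 0.3, and about 95% in both arms at an assumed r of 0.7. The remark about test-retest reliability points to a correlation above 0.5, which would make the printed changes too large, and one or two sentences would settle the matter.

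Part of this stands. The assumption is unstated, and the numbers are sensitive to it. What does not stand is the step from unstated to wrong:

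- The plan does not define 14 as an SD of scores. Its use in the between-group comparison makes that the natural reading, but it remains an inference.
- Strong test-retest reliability, given without a coefficient, concerns stability while nothing is changing. The relevant correlation is between assessments three or more months apart, in a trial of a six-month programme meant to raise activation, on a scale the plan also calls sensitive to change. A correlation of 0.5 is compatible with that description, and a lower one is not excluded.
- If the correlation is above 0.5, the printed figures overstate the detectable change and so err on the cautious side.

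**Conclusion.** No change to the plan follows. The control-arm figure is a clerical slip: 10.8 should read 10.9, a difference of 0.09 points, or 79.3% power against 80%. The missing correlation is a gap in what the power paragraph reports. With SD 14 taken as the SD of change, or with equal variances and r = 0.5, both paired figures follow from the plan's inputs apart from that last digit. The documents do not show that another value of r is right, and over an assumed range of 0.3 to 0.7 the detectable change runs from 10.4 down to 6.8 in the intervention arm and from 12.9 down to 8.4 in the control arm.

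These figures set no sample size, support no stated hypothesis and enter no planned test. The plan already says that, as a pilot, it can detect only large between-group differences. Recruitment is complete, and the analysts will estimate the correlations from the data. Writing down r would make the paragraph clearer, but it would alter neither the conduct of the trial nor its conclusions.
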